#### 8.2 Research Related Tests and Procedures

	Prior to start of pre-transplant	Post- transplant/	day 0 ^ Prior to Prior to Rituximab FT596	Post F	T596 li	nfusion	(using L	Day 0 as i	the day o	f infusion)	3, 6, and 12 months from transplant at time of SOC visit	
	Chemo	pre-i 1000			30 (± 5) minutes post infusion end	day 1	day 3	day 7	day 14	day 21	End of treatment Visit day 28	
ferritin, CRP (to hospital lab charge to research)		х									х	
Assess for toxicity (including DLTs and SRs) per Section 10			х	x	х	Х	х	х	х	x	x	Х
Six 10 ml green top tubes 	Х	Х	Х	Х		Х	Х	Х	Х	Х	Х	X (30 ml)
One 10 ml of red top tube	Х	Х	Х	Х		Х	Х	Х	Х	Х	Х	X (10 ml)
One 10 ml green top tube 					Х							
Initial Safety samples: 1 x 3 ml red top serum tube 1 x 10 ml green top tube – store frozen in TTL and batch ship to Fate	x	X (only if consented after HSCT)										
Safety follow-up: 1 x 3 ml red top serum tube 1 x 10 ml green top tube 1 x 6 ml yellow top tube – store frozen in TTL and batch ship to Fate												Х
PRA anti-HLA antibodies one 10 ml red top		Х									Х	

^ day 0 is assigned to the day of the FT596 infusion regardless of whether the infusion is given Day 30 or Day 7 post-transplant
 1- At TTL: PBMCs are isolated from the heparin/green tube at predetermined time points for PCR testing by Fate
 Refer to the Laboratory Manual for additional details

If a patient is consented after HSCT, the 60 ml green tops and 10 ml red tops research related samples associated with the pre-transplant time point are not collected.

All research samples go to the Masonic Cancer Center's Translational Therapy Lab (TTL) except for the baseline and Day 28 for ferritin and CRP testing, and the PRA anti-HLA antibody samples done prior to study treatment start and at Day 28, which are charged to research but run in the treatment center's clinical lab. If additional ferritin and/or CRP levels are collected as part of good medical care (i.e. development of signs of CRS) they are to be charged as standard of care.

**Note:** If a patient is not abiding by the required clinical care calendar (Section 8.1), the collection schedule of research related samples may be altered or deleted or discontinued on an individual patient basis, as appropriate. During follow-up no visit will be solely for research and instead be linked with a standard of care visit closest to the targeted research related time point.

It is recognized that with novel therapies as used in this study, the timing of protocol directed research samples may miss important patient specific events. For this reason, up to 3 extra samples for a total of 210 ml of blood may be collected at additional time points that are not specified above.

Samples to evaluate lymphocyte number and phenotype will be collected as detailed above for the Masonic Cancer Center Translational Therapy Lab (TTL) along with serum (red top tubes) for measure of cytokines that can reflect immune activation.

Flow cytometry analysis of a fraction of the PBMC will detect surface markers that define lymphocyte subsets (NK, NKT, B, and T cells, both CD4 and CD8), as well as intracellular markers that define regulatory T cells (Foxp3) and proliferating cells (Ki67). All remaining PBMC will be cryopreserved in 10% DMSO and stored in liquid nitrogen for future testing, if subject agreed to future storage at the time of initial consent.

Samples may be sent to laboratories outside of the University of Minnesota in cases where testing is not available internally as embedded in the patient consent form.

#### 9 Study Agents

#### 9.1 FT596

FT596 is an investigational product and can only be used and administered under an FDA-approved protocol. For the purposes of this study FT596 is provided by Fate Therapeutics.

FT596 will be provided as a cryopreserved bag, thawed at the site of administration and administered as an IV infusion via gravity. FT596 must be administered using a Fate approved intravenous administration set with an inline filter (170-260 micron).

Refer to the FT596 Storage, Handling, and Administration Guidance for additional details.

Refer to Section 7 for potential toxicities.

# 9.2 Rituximab (Rituxan or an FDA approved biosimilar, e.g. Truxima and Ruxience)

**Trade names:** Rituxan®, Truxima®, and Ruxience®

**Classification:** Monoclonal Antibody, Antineoplastic Agent

Category: Biological Response Modifier Agent

**Dosage and Administration Schedule:** For the purposes of the study, rituximab and rituximab biosimilars 375 mg/m^2 IV is administered per institutional guidelines on 2-3 days prior to FT596.

**Dose Forms and Strengths:** refer to specific product prescribing information **Availability:** Available by prescription

#### Warnings and Precautions:

- Tumor lysis syndrome administer prophylaxis and monitor renal function
- PML monitor neurologic function. Discontinue rituximab
- Hepatitis B reactivation with fulminant hepatitis, sometimes fatal screen high risk patients and monitor HBV carriers during and several months after therapy. Discontinue rituximab if reactivation occurs.
- Cardiac arrhythmias and angina can occur and can be life threatening. Monitor patients with these conditions closely.
- Bowel obstruction and perforation evaluate complaints of abdominal pain.
- Do not administer live virus vaccines prior to or during rituximab.
- Monitor CBC at regular intervals for severe cytopenias
- Pregnancy Category C

Rituximab (Rituxan and FDA approved biosimilars)						
common	less common	rare, but may be serious				

 
mild allergic reaction with first infusion (may include fever, headache, chills, itching, hives, nausea, shortness of breath)
 
	
 
allergic reaction with second and later infusions (same symptoms as under common)
 
low white blood cell count with increased risk of infection
 
cough
 
rash, itching
 
nausea
 
vomiting
 
diarrhea
 
muscle aches
 
runny nose
 
sinus infection
 
	
 
serious allergic reaction, with hives, trouble breathing, tightness in the chest or throat, heart attack, or shock
 
serious skin reaction
 
kidney damage
 
low platelet count with increased risk of bleeding
 
blockage or hole in the bowel, with abdominal (belly) pain
 
low red blood cell count (anemia) with tiredness and weakness
 
death due to allergic reaction, infection, lung damage, tumor lysis syndrome, serious skin rash, bowel obstruction, liver failure from reactivated hepatitis b, and other causes
 
				

#### **Expected Toxicities:**

Refer to individual product prescribing information for additional information:

- Rituxan® https://www.gene.com/download/pdf/rituxan\_prescribing.pdf
- Truxima® https://www.truxima.com/globalassets/truxima-dtc/pdfs/truxima-prescribing-information.pdf
- Ruxience™ http://labeling.pfizer.com/ShowLabeling.aspx?id=12090

### 10 Adverse Event Monitoring, Documentation, and Reporting

For the purposes of the study the FT596 in combination with rituximab (Rituxan and FDA approved biosimilars) is considered the investigational product.

For the reminder of the section rituximab is a blanket term for Rituxan and any FDA approved biosimilars.

Toxicity and adverse events will be classified and graded according to NCI's Common Terminology Criteria for Adverse Events V 5.0 (CTCAE) and reported on the schedule below. A copy of the CTCAE can be downloaded from the CTEP home page. (https://ctep.cancer.gov/protocoldevelopment/electronic\_applications/docs/CTCAE\_v 5\_Quick\_Reference\_5x7.pdf) An exception to the use of CTCAE will be for the assessment of cytokine release syndrome (CRS). Individual adverse events which are associated with CRS will be graded per CTCAE; however the ultimate assessment will be made using a revised grading system for CRS as presented by Lee et al (Lee 2019).

ASTCT Cytokine Release Syndrome Consensus Grading System a								
CRS Parameter	Grade 1	Grade 2	Grade 3	Grade 4				
Fever b	Temperature ≥38°C	Temperature ≥38°C	Temperature ≥38°C	Temperature ≥38°C				
With either:								
Hypotension	None	Not requiring vasopressors	Requiring vasopressors with/with-out vasopressin	Requiring multiple vasopressors (excluding vasopressin)				
And/or c	•		•	· · · · ·				
HypoxiaNoneRequiring low-flow nasal cannula d or blow-byRequiring high-flow nasal cannula, facemask, non-rebreather mask, or venturi maskRequiring positive pressure (e.g., CPAP, BiPAP, intubation and mechanical venturi mask								

#### **10.1 Adverse Event Terminology**

Adverse Event: Any untoward medical occurrence associated with the use of a drug in humans, whether or not considered drug related.

Serious Adverse Event: An adverse event is considered "serious" if, in the view of either the investigator or sponsor, it results in any of the following outcomes:

- Death
- A life-threatening adverse event
- Inpatient hospitalization or prolongation of existing hospitalization

- A persistent or significant incapacity or substantial disruption of the ability to conduct normal life functions
- A congenital anomaly/birth defect

Important medical events that may not result in death, be life-threatening, or require hospitalization may be considered serious when, based upon appropriate medical judgment, they may jeopardize the patient or subject and may require medical or surgical intervention to prevent one of the outcomes listed in this definition.

Unexpected Event: An adverse event or suspected adverse reaction is considered "unexpected" if it is not listed in the investigator brochure or is not listed at the specificity or severity that has been observed; or, if an investigator brochure is not required or available, is not consistent with the risk information described in the general investigational plan or elsewhere in the current application, as amended.

The categories for AE attribution to study treatment are as follows:

- Definite clearly related
- Probable likely related
- Possible may be related
- Unlikely doubtfully related
- Unrelated clearly not related

The following definitions are from the Masonic Cancer Center's Standard Operating Procedure (SOP) Deviation Reporting:

Major Deviation: A deviation or violation that impacts the risks and benefits of the research; may impact subject safety, affect the integrity of research data and/or affect a subject's willingness to participate in the research. Deviations that place a subject at risk, but do not result in harm are considered to be major deviations.

Minor Deviation: A deviation or violation that does not impact subject safety, compromise the integrity of research data and/or affect a subject's willingness to participate in the research.

#### **10.2 AE Documentation Requirements**

Adverse event collection for the purposes of this study will focus on events felt to be related to FT596 and rituximab or events that cannot be attributed to other causes (i.e. transplant-related, co-morbidities).

Monitoring for adverse events will begin with the first dose of rituximab through the End of Treatment visit after FT596.

Adverse event documentation for the purposes of this study will focus on

- expected toxicities felt to be related to rituximab
- expected toxicities felt to be related to the FT596
- unexpected adverse events that cannot be attributed to the transplant procedure or other causes (i.e. underlying disease, co-morbidities)

For the purposes of this study, adverse event documentation requirements in OnCore will be based on grade, expectedness and relationship to the investigational product (FT596 and rituximab):

	Grade 1	Grade 2		Gr	ade 3	Grade 4 and 5
	Expected or Unexpected	Expected	Unexpected	Expected	Unexpected	Expected or Unexpected
Unrelated Unlikely	Not required	Required	Required	Required	Required	Required
Possible Probable Definite	Not required	Required	Required	Required	Required	Required

After the End of Treatment visit, monitoring for adverse events will become less frequent based on the schedule in Section 8.1 and only events that are unexpected and at least possibly related to FT596 will be documented upon knowledge.

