#### 1.2 Secondary Objectives

- To evaluate the adverse events related to FT596 administered post auto-HSCT in combination with rituximab (Rituxan or an FDA approved biosimilar, e.g. Truxima and Ruxience).
- To determine preliminary efficacy based on progression free survival (PFS) and relapse/progression at 12 months post auto-HSCT.
- To determine the incidence of non-relapse mortality at 100 days and 1 year post auto-HSCT.

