#### 6.1.2 FT596 Administration

FT596 is given 2-3 days after rituximab; however, it may be delayed for up to 7 days until all rituximab infusion related toxicities resolve to ≤Grade 1.

**FT596 Thawing Overview:** FT596 is provided in one or more cryopreserved bags based on the patient's dose level. The correct number of bags are transferred to the site of infusion using a validated cooler. Thawing occurs on the unit just prior to administration. When dose level requires multiple bags, bags are thawed sequentially. FT596 is stable for up to 60 minutes post-thaw. Administration of the cell product must begin within 60 minutes of thawing.

**FT596 Infusion guidelines:** FT596 must be administered via gravity using a Fate approved IV administration set with an in-line filter. Total infusion time per bag is less than 10 minutes. If multiple bags are used, a short delay between infusions occur to allow for product thawing. To infusion 3 bags of cells (the maximum required for the dose levels in this study), total infusion time from the start of the 1st bag to the end of the last bag would be 30-40 minutes.

Complete information is provided in the FT596 Storage, Handling, and Administration Guidance

The end of administration time should be recorded after the rinse step has been completed. When the study drug administration has been completed, discard the empty study drug bag/tubing in accordance with local site policy.

**Pre-Medications**: Prior to administration of FT596 and 4-6 hours later, patients should be pre-medicated with acetaminophen 650 mg orally (PO) and diphenhydramine 25 PO. Corticosteroids should not be used as pre-medication for FT596.

**Vital Signs:** Vital signs (temperature, systolic and diastolic blood pressure, heart rate, and respiration rate) are performed in association with the FT596 infusion at the following time points: within 15 minutes of the infusion start, at 10 ( $\pm$ 5) minutes during infusion, and every 15 ( $\pm$ 5) minutes for 1 hour after the end of the last administered bag of FT596.

**Collection of research sample 30 (±5) minutes after the last bag of FT596** is infused per Section 8.2. One or more bags are given depending on the dose level.

**Monitoring for Infusion Related Reactions:** All patients are monitored for signs of an infusion related reaction. The highest grade infusion reaction for the FT596 infusion must be documented (and if applicable reported as a dose limiting toxicity and/or an SAE).

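### AE relationship is defined against FT596 plus rituximab as one product, while the first secondary objective and the late-follow-up rule refer to FT596; no per-agent causality record and no definition of the FT596-related AE summary is given

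*Combined protocol and SAP*

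**What the plan says.** **Attribution target.** The opening of section 10 says that "the FT596 in combination with rituximab (Rituxan and FDA approved biosimilars) is considered the investigational product". Section 10.1 then gives one five-level scale, introduced by "The categories for AE attribution to study treatment are as follows". Section 10.2 ties documentation to grade, expectedness and "relationship to the investigational product (FT596 and rituximab").

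**Window.** Section 10.2 states: "Monitoring for adverse events will begin with the first dose of rituximab through the End of Treatment visit after FT596". Section 6.1.2 sets the gap between the agents: "FT596 is given 2-3 days after rituximab; however, it may be delayed for up to 7 days". That delay allows rituximab infusion toxicity to settle to Grade 1 or below. Under section 6.6, FT596 is not given if the toxicity has not settled by 7 days after rituximab.

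**What the results are meant to describe.** The first secondary objective (section 1.2) is "To evaluate the adverse events related to FT596 administered post auto-HSCT in combination with rituximab". After the End of Treatment visit, section 10.2 changes the criterion: "only events that are unexpected and at least possibly related to FT596 will be documented upon knowledge".

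**Analysis.** Section 12.3 says that safety and toxicity rates are summarised descriptively. It does not say which events make up an FT596-related summary, over what window, or judged against which agent.

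**The concern.** The relationship scale answers whether an event is due to the combination. The secondary objective, on its natural reading, asks whether it is due to FT596. A rituximab reaction that occurs before any FT596 is given is correctly rated as related to the combined product, although FT596 cannot have caused it. After FT596, a cytopenia or infection rated as related to the combination carries no record of which agent the investigator suspected.

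This matters because section 7 says there are no clinical data on FT596, so the descriptive AE tables will be early evidence on its toxicity. Rituximab's toxicity is already described: section 9.2 lists mild allergic reactions at first infusion as common, low white cell count with infection risk as less common, and low platelets and anemia as rare. If both agents share one relationship rating, known rituximab toxicity could be read as FT596 toxicity. Per-event causality judgements are hard to reconstruct reliably once the trial is over.

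**Working it through.** The plan states no FT596-related AE rate and no rituximab reaction rate, so there is no figure to reproduce. The check is mainly textual.

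**Step 1: the sections side by side**

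| Place | Relationship is to |
|---|---|
| Section 10, opening | FT596 with rituximab, as one product |
| Section 10.1, attribution scale | study treatment |
| Section 10.2, up to End of Treatment | FT596 and rituximab together |
| Section 10.2, after End of Treatment | FT596 |
| Section 1.2, first secondary objective | FT596, given with rituximab |
| Section 12.3 | not defined |

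The target changes within section 10.2, and no section asks for a rating per agent.

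**Step 2: which events are recorded.** The table in section 10.2 requires all Grade 2 to 5 events in both the related and unrelated rows, and no Grade 1 events. Up to End of Treatment, then, relationship does not decide what is captured. It matters for how events are later summarised. Mild (Grade 1) rituximab reactions are not required. Grade 2 or higher reactions before FT596 are recorded, and section 6.1.2 foresees them.

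**Step 3: how much of the window precedes FT596.** With a gap of g days and the End of Treatment visit at day 28 after FT596 (section 8.1), the share is g / (g + 28):
- g = 2: 2/30 = 6.7%
- g = 3: 3/31 = 9.7%
- g = 7: 7/35 = 20%

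**Step 4: illustration on assumed rates.** Let f be the true share of patients with an FT596-related AE and r the share with a documented rituximab-only event. Take them as independent, and suppose that the summary uses the combined rating with no onset filter. None of these values or assumptions comes from the documents.
- Apparent rate = 1 − (1 − f)(1 − r)
- Increase = r(1 − f)
- f = 20%, r = 10%: 1 − 0.8 × 0.9 = 28%, an increase of 8 points. This is 12 × 0.08 = 1.0 extra patient of 12, or 18 × 0.08 = 1.4 of 18.
- f = 20%, r = 30%: 1 − 0.8 × 0.7 = 44%, an increase of 24 points. This is 12 × 0.24 = 2.9 of 12, or 18 × 0.24 = 4.3 of 18.
- Over f = 10% to 30% and r = 5% to 30%, the increase runs from 0.05 × 0.7 = 3.5 points to 0.30 × 0.9 = 27 points.

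The chance of at least one patient with a rituximab-only event is 1 − (1 − r)^n. At r = 5% it is 46% for n = 12 and 60% for n = 18. At r = 10% it is 72% and 85%. The sample sizes are the likely and maximum enrolment per component in the Synopsis.

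**Step 5: what an onset filter would leave.** If onset dates are recorded, events before FT596 can be removed afterwards. Events after FT596 that either agent could cause cannot. The documents give no basis for putting a number on that remainder.

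**The case against.** The case on the other side is substantial.

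- **Section 10.2 already presupposes a judgement per agent.** It lists expected rituximab toxicities and expected FT596 toxicities as separate areas of focus. This stands, but those items describe emphasis. The operative sentence and table have one relationship axis, and the item on unexpected events is not split by agent.
- **The AE form is not shown.** It is built in OnCore and approved by the principal investigator and the biostatistician (section 11.2), so it may have two fields. True, but the protocol does not require them.
- **The objective mentions the combination.** Attribution to both agents is a permissible reading of section 1.2. It fits less well with the later rule in section 10.2, which names FT596 alone.
- **FT596 infusion reactions are captured by product.** Section 6.1.2 requires the highest grade for the FT596 infusion, so the most obvious overlapping toxicity is already separated.

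A reader might also infer several stronger points that the documents do not support:

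- *Rituximab reactions will inflate a planned FT596-related AE rate.* Section 12.3 defines no such rate. This is a risk left open, not a certain result.
- *The rule after End of Treatment cannot be applied.* It can: it directs the investigator to judge relationship to FT596 at that time.
- *A contaminated related-AE rate goes to the FDA before Component 2.* Section 6.3 lists a summary of adverse events, DLTs, stopping rule events and SAEs, and the Synopsis names DLT and stopping rule events. Neither mentions a related-AE rate.
- *Early and late rates would be compared across a changed criterion.* No such comparison is planned, and late collection is limited to unexpected events in any case.
- *Dose finding is affected.* The DLT window starts at FT596 dosing (section 12.1), and sections 6.4 and 10.4 exclude pre-FT596 events.

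**Conclusion.** The concern holds as a mismatch between the attribution rule and the secondary objective, together with a missing analysis definition. Sections 10 to 10.2 state a combined attribution rule; they do not merely leave the matter open. Neither section 10 nor section 12.3 supplies the per-agent record or the definition that would let the FT596-related events be summarised.

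The consequence is limited. The descriptive summary of related AEs could include Grade 2 or higher rituximab-only events, and post-FT596 events with two plausible causes could not be reliably separated later. The 28% to 44% figure shows the possible scale under assumed rates, independence and no onset filter; it is not an estimate for this trial. Pre-FT596 events do not alter the MTD, DLT or stopping-rule results. The point is a low-cost improvement, not a flaw that threatens the trial.

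**What to change.** 1. **Sections 10.1 and 10.2:** record relationship separately for FT596 and for rituximab, using the same five categories. Keep the combined product definition for expedited reporting.
2. **Section 12.3:** define FT596-related AEs as events with onset after the start of the FT596 infusion and a relationship to FT596 of possible, probable or definite.
3. **Tables:** show rituximab-only events, and events between rituximab and FT596, separately from the FT596-related summary.

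The cost is one more field on the AE form, one more table, and one more judgement per event. That judgement will be imperfect where the toxicities overlap, notably for cytopenia and infection. Recording it when the event occurs is still more reliable than reconstructing it later.

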#### 6.7 Duration of Study Participation

Follow-up for disease and survival endpoints continues through 1 year post-transplant.

Direct study participation ends approximately 30 days after the last FT596 infusion and once an End of Treatment visit has occurred.

Clinical information including disease status and potential late toxicities associated with FT596 will be abstracted from follow-up visits associated with the transplant at Day 100, Day 180, Day 270 (if done), and Day 365. After Day 365 (1 year), the patient's follow-up will transfer to a designated long-term follow-up protocol per Section 6.8.

Rituximab or the FDA approved biosimilar may continue (independent of this study) per institutional practice.

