## 7.6 Myelosuppression, Immunosuppression, Bone Marrow Failure, and Infections

Therapies used for the treatment of hematologic malignancies have been reported to cause myelosuppression (neutropenia and/or thrombocytopenia), leukopenia, anemia; and in some cases, bone marrow failure. Hematologic cytopenias could be further compounded by other factors such as underlying disease, concurrent illnesses and concomitant medications.

Close monitoring of complete blood count (CBC) and for the development of infections is strongly recommended. In general, management including transfusion support and use of growth factors, should be done in accordance with standard institutional practice.

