### 8.1 Required Clinical Care Evaluations

	Screening prior to	Post-Transplant Confirmation of	Day of FT596	Post FT596 Infusion (using Day 0 as the day of infusion)				Abstract from patient's EMR at	3, 6, and 12 months from		
	Transplant	Continuing Eligibility (approximately Day 21 for Component 1)	approved biosimilar, e.g. Truxima and Ruxience) Infusion (-3 day window for labs and assessment)	Infusion (Day 0^)	day 2	day 7	day 14	day 21	EOT visit day 28	each SOC visit until the 3 month post-transplant	transplant at the time of SOC visit
Consent	X 		-								
Screening Assessment	Х										
Brief Medical Assessment				Х	Х	Х	Х	Х	Х		
Medical History	Х	Х									Х
Concomitant Medications	Х			Х							
Assess Venous Access		Х									
Physical Exam	Х	Х	Х								Х
ICANS (neurotoxicity) monitoring – refer to Section 7.4		X		Х		X 	X 	X 	X 		X
Weight	Х	Х	X								
Height	Х										
Vitals and Pulse Oximetry	Х	Х	X	Х					X 		
Toxicity Assessment	Х	Х	Х	Х	Х	Х	Х	Х	Х	Х	Х
CBC, diff, plt	Х	Х	X	Х	Х	Х	Х	Х	Х	Х	Х
Basic metabolic panel (BMP) 				Х	Х	Х	Х	Х			Х
Comprehensive metabolic panel (CMP) or equivalent  plus magnesium, phosporus	X	X	X						X	X	
eGFR	Х	Х									
Urine or serum pregnancy test for WOCBP 	х	X									
If pt develops cytokine release syndrome (CRS): CRP, ferritin and, if testing available, IL-6				If CRS is s At diagnos outpt visit t	uspecter is docun until reso	d obtain nent CR plution of	CRP, ferr P, ferritin a CRS. Re	itin and IL- and IL-6 lev fer to Secti	6 levels vels 3 x week on 7.3.	ly if inpt or at every	
If pt develops neurotoxicity				Refer to Se	Section 7.4 for FDA recommended testing 						

	Screening prior to	Post-Transplant Confirmation of	Day of Rituximab Day of Rituxan or an EDA ET59		Day of Post FT596 Infusion (using Day 0 as the day of infusion)			Abstract from patient's EMR at	3, 6, and 12 months from		
	Transplant	Continuing Eligibility (approximately Day 21 for Component 1)	approved Infusion biosimilar, e.g. (Day 0^) Truxima and Ruxience) Infusion (-3 day window for labs and assessment)	day 2	day 7	day 14	day 21	EOT visit day 28	each SOC visit until the 3 month post-transplant	transplant at the time of SOC visit	
Disease staging	Х	Х									Per SOC
CXR or chest CT scan	X										
PFTs⁵	Х										
EKG	Х										

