#### **12.3 Statistical Analysis**

The MTD will be determined in Component 1 and Component 2 per the design. All other endpoints including safety, progression-free survival, relapse, non-relapse mortality, toxicity rates and other clinical activity will be estimated descriptively. This will include simple frequencies, proportions, means, standard deviations/standard errors, medians and ranges.

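### After the day-28 visit, expected, non-serious FT596-related events need not be recorded as adverse events; this conflicts with Sections 6.7 and 6.8 and lowers any AE rate reported beyond that visit

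*Combined protocol and SAP*

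**What the plan says.** The first secondary objective (Section 1.2) is "To evaluate the adverse events related to FT596 administered post auto-HSCT in combination with rituximab", with no time window. Section 12.3 says that "toxicity rates and other clinical activity will be estimated descriptively", again with no window.

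Section 10.2 sets two collection rules. The first period is defined by "Monitoring for adverse events will begin with the first dose of rituximab through the End of Treatment visit after FT596", and the Section 8.1 calendar places that visit at "EOT visit day 28" after the infusion. Within it, the 10.2 table requires every event of Grade 2 or higher, whatever its expectedness or attribution. After it, "only events that are unexpected and at least possibly related to FT596 will be documented upon knowledge".

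Section 10.1 calls an event unexpected "if it is not listed in the investigator brochure or is not listed at the specificity or severity that has been observed". The investigator brochure is therefore the reference list, and it is not among the documents.

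Other sections treat the later period differently. Section 6.7 says "potential late toxicities associated with FT596 will be abstracted from follow-up visits associated with the transplant" at Day 100, 180, 270 (if done) and 365. Section 6.8 has delayed conditions, including new or worsening neurologic disorders and new hematologic disorders, documented and reported to the FDA. Neither section limits this to unexpected events.

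**The concern.** The post-EOT rule filters on expectedness, so it can drop events that are clearly caused by the product. An unrelated Grade 2 event on day 27 after FT596 is required. An expected, non-serious Grade 3 event on day 40 is not, even when judged definitely related.

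Section 7 states that there are no clinical data on FT596 and that its risk information is extrapolated from other cell products. Any list of expected terms would therefore rest on little direct experience. Section 7.6 discusses cytopenias and infections as potential risks and says "Close monitoring of complete blood count (CBC) and for the development of infections is strongly recommended", so these are plausible candidates for the expected list.

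Two things are at stake: the FT596-related AE profile beyond EOT, and the adverse-event part of the summary that Section 6.3 promises the FDA before Component 2 opens.

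**Working it through.** The plan gives no AE rate to reproduce. The check has four parts.

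**1. When the restricted rule applies.** FT596 is given on Day 30 (Component 1) or Day 7 (Component 2), with a +3 day window, and EOT is 28 days later.

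- EOT in post-transplant days: 30 + 28 = 58 and 7 + 28 = 35 (61 and 38 at the end of the window).
- Share of post-infusion time to Day 100 under the restricted rule: (100 − 58)/(100 − 30) = 42/70 = 60%; (100 − 35)/(100 − 7) = 65/93 = 70%.
- Share to Day 365: (365 − 58)/(365 − 30) = 307/335 = 92%; (365 − 35)/(365 − 7) = 330/358 = 92%.

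**2. What is still recorded after EOT.**

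| Event with onset after EOT | Where covered | Recorded? |
|---|---|---|
| Any SAE | 10.3, no expectedness limit | Yes |
| Any death | 10.5 | Yes |
| Stopping-rule event (mortality or Grade III–IV acute GVHD by Day 100; Grade 4 lymphopenia at Day 100) | 6.4, 10.4 | Yes |
| Unexpected and at least possibly related, including worse than the brochure lists | 10.1, 10.2 | Yes |
| New or worsening neurologic disorder, new hematologic disorder | 6.8 | Yes, as a delayed condition |
| Expected, related, non-serious, none of the above | 10.2 against 6.7 | Not required as an AE by 10.2; abstracted as a late toxicity by 6.7 |

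Only the last row is in dispute. Section 8.1 schedules a toxicity assessment at the record abstractions up to 3 months and at 3, 6 and 12 months. The 8.2 entry for the later visits says to assess toxicity per Section 10, which leads back to the restricted rule. Two sites could each follow the protocol and hold different data.

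**3. Effect on a reported rate (illustration).** The documents give none of these inputs, so all are assumptions. Let e be the risk of a first expected toxicity by EOT, l the risk of a first one afterwards among those without it, and s the share of late events recorded by another route.

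- True one-year rate: 1 − (1 − e)(1 − l).
- Recorded rate: 1 − (1 − e)(1 − l·s).
- Shortfall: (1 − e)·l·(1 − s).

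With e and l each between 10% and 30%:

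- s = 0: from 0.7 × 0.1 = 7 points to 0.9 × 0.3 = 27 points.
- s = 0.5: 3.5 to 13.5 points.
- s = 1: 0 points.

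For any rate that ends at EOT the shortfall is 0.

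**4. The FDA summary.** Take the 12 patients that Section 12.2 calls most likely and the minimum spacing in 12.1, with no death or dropout. Infusions then fall on study days 0, 28, 56, 84, 112, 126, 154, 182, 196, 224, 252 and 266, and the last 28-day window closes on day 294.

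- Post-infusion patient-days by then: 12 × 294 − 1,680 = 1,848.
- Under full collection: 12 × 28 = 336.
- Under the restricted rule: 1,848 − 336 = 1,512, or 82%.

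This too is a share of time, not of events.

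**The case against.** The strongest reply is that little is lost. Most late events that matter clinically reach the database by the other routes in the table, and the Section 6.3 summary includes SAEs and stopping-rule events as well as AEs. Cell counts and ICANS monitoring are scheduled at 3, 6 and 12 months. A cytopenia that starts before EOT at Grade 2 or higher is already recorded. If the brochure lists few terms, most late events count as unexpected and are documented. All of this stands, and it narrows the point to expected, non-serious, related events with onset after EOT.

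It does not close the gap. None of those routes requires a non-serious Grade 3 infection to be entered as an AE if the brochure lists it as expected. The same holds for a new late neutropenia or thrombocytopenia, unless it counts as a new hematologic disorder under 6.8. Section 6.7 would reach both, but it conflicts with 10.2 and does not say how what it abstracts enters the AE analysis.

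A reader might infer that expected late toxicities are never recorded, or that late neurotoxicity disappears. The documents do not support either. Section 7.4 calls neurotoxicity rare and generally not believed to be an NK-cell effect, so it may well be unexpected, and 6.8 names neurologic disorders. Section 7.3 makes a similar statement about CRS.

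**Conclusion.** The point holds for one class of events: expected, non-serious and at least possibly related to FT596, with onset after EOT. For these, 10.2 conflicts with 6.7 and 6.8, and a rate reported beyond EOT from 10.2 data would be too low. Under the assumptions above the shortfall runs from 0 to 27 points. Where it falls depends on the brochure's list, the true late risk and the share captured elsewhere, none of which the documents give.

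A reader might take the 92% as the proportion of events missed, or conclude that the MTD is unsafe. Neither follows. The percentages are shares of follow-up time. The DLT window is 28 days after FT596, so it ends at EOT, and Component 2's added engraftment criterion at post-transplant Day 28 falls before its EOT. The dose-finding model, the MTD and AE rates through EOT are unaffected.

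This is a cheap improvement to a secondary objective, not a threat to the primary one.

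**What to change.** In Section 10.2, keep the present post-EOT rule and add to it. After EOT, document:

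- (a) unexpected events at least possibly related to FT596, of any grade, as now; and
- (b) Grade 3 or higher events at least possibly related to FT596, whether expected or not.

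Apply this at the toxicity assessments already scheduled in 8.1 and 8.2 through 12 months. Part (b) must not replace part (a): a Grade 3 threshold alone would lose the unexpected Grade 1–2 related events that are now collected, which are the likeliest new signals for a product without clinical data.

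Reconcile 10.2 with 6.7 and 6.8 so that all three describe the same late collection. In 12.3, state that all-grade AE rates run through EOT and that later rates cover only the events collected under the post-EOT rule.

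The cost is a wording change and a few more AE entries from visits already abstracted. No new visit or test is needed.
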